##### *d. Study outcomes/endpoints*

The study outcome will be a body of evidence that supports our hypothesis: that interactions with ADL content inside the graphical interactive virtual world, DevaWorld, supports completions of actual ADLs.

DevaWorld's feasibility (Aim 1)

Successful primary outcomes are >55% DWS-participation rate and a statistically significant difference between assessments of DWS-participation and non-participation, indicating tolerability and acceptability of routine DWS.

DevaWorld as an assistive tool for preparing and completing ADLs. (Aim2)

Successful secondary outcomes are:

- a reduction in ADL-related care challenges compared to baseline
- reduced time spent on ADLs compared to baseline
- a reduction in negative response behaviors associated with the ADL
- greater interest in the ADL
- a positive shift in care staff attitudes

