nor exclude participation based on cognitive test scores, however, participants will be given the MMSE test (20) at baseline. Anonymized scores may be referenced in post-study discussions. The participants will have had challenge(s) completing one or more ADLs in the previous month, as discussed at staff meetings, referenced in care plans, or observed/experienced by direct care staff. Ineligible residents are those with significant

non-AD/ADRD neurological, psychiatric, or physical impairment or those who are totally dependent upon others for ADLs.

Other specifications:

- Understand English or Russian.
- Are verbal
- Can sit comfortably for at least 15 minutes in a chair/wheelchair at a table or propped up in bed or princess chair with a tray table
- Are not known to be in pain
- Have good vision, or good corrected vision (i.e., glasses)
- Have good hearing, or good corrected hearing (i.e., aids)
- May sometimes have anxiety or agitation when undertaking ADLs.

Exclusion criteria

- Persons subject to a legal protection order
- Current or planned participation in other research involving neuropsychological evaluations and/or drug trial, up until the end of the current study.
- Informed consent not signed
- Compatible caregiver not found

Staff

Staff are experienced and motivated; are employed at the test site; assist with ADLs will have ADL care experience with residents prior to the study. Their role is to support the participant during a DWS and help them have an optimal session with the app. Staff will receive training on this. After the DWS, staff will assist the resident with their usual ADL routine at times suited to the resident. They will also fillout reports each day.

*ii. List and describe each of the study procedures, assessments, and activities.*

- Initiation session with staff to outline baseline study protocol.
- In the first two weeks of the study to establish baseline, dyads will undertake usual ADL care, i.e., without the DevaWorld Session (DWS) intervention. Staff schedule during baseline:

Mon 40m	Tue 40m	Wed 40m	Thu 40m	Fri 40m
Res A Mouth Care	Res A Mouth Care	Res A Mouth Care	Res A Mouth Care	Res A Mouth Care
Res B Mouth Care	Res B Mouth Care	Res B Mouth Care	Res B Mouth Care	Res B Mouth Care
Res C Mouth Care	Res C Mouth Care	Res C Mouth Care	Res C Mouth Care	Res C Mouth Care
Res Mouth Care	Res Mouth Care	Res Mouth Care	Res Mouth Care	Res Mouth Care
Reporting before end of shift				

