- Following baseline and prior to the intervention phase, participating staff will take part in group training, with extra support as needed.
- During the intervention phase, a period of six weeks, the same dyads (or as close to same as is practical) will be assigned a schedule incorporating DWS followed by the same ADL routine as baseline.
- Each resident-participant will have two DWS per week. Staff-participants will spread this load across their shifts, averaging eight DWS sessions per 5-day week. We anticipate that session durations will average five minutes with variability according to resident-participants' individual interest levels on a given day. Staff schedule during study:

Mon 1h 10m	Tue 55m	Wed 1h 10m	Thu 55m	Fri 1h 10m
Res A DWS	Res A Mouth Care	Res A DWS	Res A Mouth Care	Res A Mouth Care
	Res B Mouth Care		Res B DWS	Res B Mouth Care
Res A Mouth Care	Res C DWS	Res A Mouth Care		Res C DWS
Res B DWS		Res B Mouth Care	Res B Mouth Care	
Res C Mouth Care	Res C Mouth Care	Res C Mouth Care	Res C Mouth Care	
Res B Mouth Care	Res D Mouth Care	Res D DWS	Res D Mouth Care	Res D DWS
Res C Mouth Care				
Res D Mouth Care		Res D Mouth Care		Res D Mouth Care
Reporting				

- Procedure for running a DWS

- **Initiating a session:**

Prior to the ADL, the dyad will sit in a quiet nook or the resident's bedroom with appropriate lighting. The care staff will ask the resident if they are comfortable (e.g. need a drink, need to go to the toilet, is comfortably dressed, has glasses and hearing aids in place).

To initiate the session, the care staff will open DevaWorld on the tablet device and invite resident to join.

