## IX. Analysis Plan

*Describe statistical analysis methods as appropriate. For example, will intention-to-treat methodology be used in the analysis? Will there be any sample stratification?*

- Thematic and sentiment analysis of tablet-recorded spoken and visual exchanges during DWS and post-session comments
- Statistical and text analyses of questionnaire responses
  - Statistical Analysis Plan
    - Assessment inventories with scores on the inventory's scale
    - Measuring mean value and standard deviation for the group
    - Complete a superiority statistical test
    - P-values calculated by t-test, 1 sided

HIPAA-compliant data capture software; eg REDCap, will be used to create the database and analyses. <https://www.project-redcap.org/>

Data will be reported graphically or with summary measure (e.g., means and standard errors or median and 95% confidence intervals), and subjected to statistical analysis when appropriate. Completion rates and grades scores will be presented as proportions and percentages.

ADCS-ADL scores will be compared from end of baseline to biweekly scores to the end of intervention and may be analyzed using a paired Student's t-test or the Wilcoxon signed-rank test if the data are not normally distributed.

Completion rates will be the percentage of all dyads who complete the entire eight weeks of study. The ratio of positively graded scores per dyad will be calculated to obtain the level of satisfaction of dyads and indicate the acceptability of DWS.

Aim 1: Successful primary outcomes are >55% completion rate and a statistically significant difference between assessments of completers and non-completers, indicating tolerability and acceptability of routine DWS.

Aim 2: The secondary outcome is to determine the feasibility of DevaWorld as an assistive tool for preparing and completing ADLs. Improved dyad outcomes are less time to complete ADLs, a reduction in negative response behaviors associated with the ADL, greater interest in the ADL, Care staff indicates tasks are easier than before.

Outcomes measures for baseline and intervention will be the same. As the score sheets cover a broader range of ADLs than those depicted in DW, overall and individual ADL scores will be analyzed and subjected to statistical tests. Our null hypothesis will be no statistical differences between ADL scores during the intervention and baseline phases

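### The >55% completion mark for Aim 1 counts dyads lost in the two usual-care weeks against DWS, a conservative and modest bias, and section V.d names a different rate for the same mark

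*Combined protocol and SAP*

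**What the plan says.** Section IX (Analysis Plan) gives the only definition of the rate that can be computed: "Completion rates will be the percentage of all dyads who complete the entire eight weeks of study". The Aim 1 rule follows in the same section: "Aim 1: Successful primary outcomes are >55% completion rate", together with a completer versus non-completer comparison. The result is read as "indicating tolerability and acceptability of routine DWS".

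Section VI.c.ii (study procedures) splits the eight weeks in two. For the first two weeks, "dyads will undertake usual ADL care, i.e., without the DevaWorld Session (DWS) intervention". The sessions come afterwards: "During the intervention phase, a period of six weeks, the same dyads" follow a schedule that includes DWS. Sections VI.c.ii and VI.c.iii place staff training on the app after baseline.

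Section V.d (Study outcomes/endpoints) puts the same threshold on a differently named quantity: "Successful primary outcomes are >55% DWS-participation rate". It gives no numerator, denominator or time window.

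No section replaces dyads lost during baseline, removes them from the denominator, or separates reasons for leaving.

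**The concern.** The rate is offered as a measure of how DWS is tolerated, but for two of its eight weeks no DWS takes place. A dyad that leaves in those weeks can show nothing about tolerance of DWS, yet it stays in the denominator as a non-completion. The hurdle for DWS then depends on how many dyads happen to leave before it starts.

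The rate is half of the primary success rule for Aim 1, and its estimate is a main product of a feasibility study. Two things are at stake: the meaning of the reported percentage and, in a narrow range, the pass or fail result. The different name in section V.d adds a second difficulty. A reader cannot tell whether 55% applies to staying in the study or to taking part in sessions.

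**Working it through.** **Inputs**
- 32 residents needed, 20% dropout, 40 enrolled: section VI.a.i.
- Rate, population and window: section IX. I read all dyads as all enrolled dyads, one per resident, hence 40.
- Two weeks without DWS, then six with: section VI.c.ii.
- The documents give no dropout rate for the baseline weeks, so the number lost there, *b*, is varied.

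**The plan's own figure.** 32/(1 − 0.20) = 40, which reproduces the enrolment target.

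**At the planned dropout.** Eight losses give 32/40 = 80% wherever they fall. Completion of the DWS phase is 32/(40 − *b*): 80% if *b* = 0, 32/36 = 88.9% if *b* = 4, and 100% if *b* = 8. The written rate cannot tell these cases apart.

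To place the losses in time, assume a constant hazard. With eight-week completion S, the share lost in weeks 1-2 is 1 − S^(2/8), and completion among dyads reaching DWS is S^(6/8). At S = 0.80:
- lost before DWS: 1 − 0.80^0.25 = 5.4%, or 2.2 of 40;
- completion among dyads reaching DWS: 0.80^0.75 = 84.6%, against 80.0% as written, a gap of 4.6 points.

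Both figures are well above 55%.

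**When the verdict can change.** 22/40 is exactly 55.0% and fails, so the written rule needs 23 completers. A six-week denominator of 40 − *b* needs the smallest count above 55% of that number.

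| Lost in baseline | Enter DWS phase | Retention demanded of them as written | Needed on six-week denominator | Completer counts where the verdicts differ |
|---|---|---|---|---|
| 0 | 40 | 23/40 = 57.5% | 23 | none |
| 2 | 38 | 23/38 = 60.5% | 21 | 21-22 |
| 4 | 36 | 23/36 = 63.9% | 20 | 20-22 |
| 8 | 32 | 23/32 = 71.9% | 18 | 18-22 |

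Example: four dyads leave in baseline and 22 of the other 36 finish. The written rule gives 22/40 = 55.0%, a fail. The six-week rate is 22/36 = 61.1%, a pass.

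**Chance of passing (binomial, assumed DWS-phase retention).**
- Retention 65%, *b* = 4: P(X ≥ 23 of 36) = 0.63 as written, P(X ≥ 20 of 36) = 0.91 on the six-week denominator.
- Retention 80%, *b* = 4: 0.993 against more than 0.999.

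The 65% is not in the documents. With four baseline losses it implies 0.65 × 36/40 = 58.5% eight-week completion, close to the mark by construction.

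**Effect of moving the mark.** Under constant hazard, 55% over six weeks corresponds to 0.55^(8/6) = 45% over eight weeks.

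**The case against.** The strongest case on the other side has four parts.

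1. *The effect is immaterial at the plan's own inputs.* A changed verdict needs at most 22 completers of 40, a loss of at least 18/40 = 45%, more than twice the planned 20%. This stands and limits the weight of the point. The reported percentage is still misattributed when the verdict is safe.

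2. *The bias is conservative.* Baseline losses can only lower the rate, so they cannot create a false success, and retention of all dyads is a reasonable measure for an eight-week feasibility study. This also stands, and it is why the eight-week figure should be kept. It does not make that figure a measure of DWS tolerability.

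3. *Constant hazard probably overstates baseline loss.* Withdrawal after seven consecutive days of refused sessions (section VI.c.ii) can operate only once DWS has begun, and screening favours willing residents (section VI.a.iii). This is fair. The 5.4% is an illustration, not an estimate.

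4. *Section V.d may govern.* If the criterion is a participation rate, the problem may not arise. But section V.d supplies nothing to compute, so this is a reason to reconcile the two sections.

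A reader might also infer that the error is largest near 55%. It is not. Under constant hazard the absolute gap S^0.75 − S is 8.9 points at S = 0.55 and peaks at 10.5 points near S = 0.32, while the relative error keeps growing as S falls. Only the consequence is concentrated near the mark.

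**Conclusion.** The mismatch is real. The rate covers two weeks in which DWS cannot be tolerated or refused, and the same 55% carries a different, undefined name in section V.d.

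Its size is modest. At 20% dropout and an assumed constant hazard, the written figure is 80.0% against 84.6%, with no effect on the verdict. The result can flip only when at least one dyad leaves in baseline and no more than 22 of 40 complete. If nobody leaves in baseline, the bias is zero.

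One might infer that Aim 1 is likely to fail for reasons unrelated to DWS, or that the 0.63 against 0.91 contrast is the expected cost. The documents support neither: they give no baseline dropout rate, the 65% retention is assumed, and their own dropout figure leaves a wide margin above 55%. The point justifies a change of wording before data are seen and does not undermine the design.

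**What to change.** Before any outcome data are seen, put one definition of the 55% criterion in both section V.d and section IX. Suggested text: *The DWS completion rate is the percentage of dyads entering the six-week intervention phase (at least one DWS scheduled) that complete those six weeks. Dyads that refuse every session are counted in the denominator. Success requires a rate above 55%.* Entry is set by scheduling and not by acceptance, so refusers cannot drop out of the count.

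Beside it, as study feasibility, report eight-week retention over all enrolled dyads and the number lost before the first scheduled DWS.

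Cost: wording in two sections and one extra count, with no new data or participants. There are two downsides to state openly. The denominator falls slightly below 40. An unchanged 55% over six weeks is also a looser mark than 55% over eight (about 45% eight-week completion under constant hazard), so the sponsor should either justify keeping 55% or reset it.

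One limit remains. The revised rate still measures staying in the study. A resident who often declines sessions, but never on seven consecutive days, can still count as a completer. If participation in sessions is what section V.d intends, it needs its own numerator and denominator.

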**Consent/No consent:**

As the app opens, the care staff will obtain verbal consent (resident uses affirming, positive words or sounds) or non-verbal consent (resident smiles/nods/leans toward the tablet/touches care staff in a positive way/agrees to touch the screen either independently with care staff's support).

If no consent, the caregiver will reapproach in 3-5 minutes, again check if the

person is comfortable, and make any adjustments to improve comfort. Care staff will seek consent again. If consent is not given a second time, the DWS will be dropped and the usual ADL routine will begin.

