**Ongoing Participation or Refusal:**

Staff will record the resident's attitude to the DWS in their daily report. The research team will review these reports daily.

Refusal may be communicated verbally (using negative or anxious words or sounds) or non-verbally (shrugging, shaking head, pushing the tablet away, refusing to put hand to the tablet, not permitting the care staff to hold their hand to support screen tapping, turning their body away, looking away from the app, passive disinterest

If a resident-participant decides that they no longer want to be involved in the study, not just the DWS session for the day, they will be offered DWS sessions daily. After 7 consecutive days of refusals, they will be withdrawn from the study.

(Guidance on the Process Consent method is covered during training and is described below.)

- Plan for 5 mins per session
- Upon consent, care staff initiates the DWS and guides the resident to the part of DevaWorld where the interactive ADL will be explored
- Following the resident's lead in pace and interest, the dyad focuses on helping the DevaWorld characters (male or female) to manage self-care activities in DevaWorld's bathroom and getting him/her ready for bed.
- The session will end when the resident seems ready
- Upon completion of a session, the care staff assists the resident, if needed, to select an emoticon on the end screen before ending the DWS.
- After completing the DWS, the care staff will initiate the planned ADL task, and observe their resident's interactions, cooperation, mood and any behavioral responses.
- Process Consent (21). This method is used during DevaWorld sessions.
  - Staff participant checks consent prior, during and after DW session.  
If Subject indicates their withdrawal of consent, Staff stops and lets the resident withdraw before or during the activity
  - If the resident no longer wants, or is no longer able, to be involved.  
The staff observes residents wishes (verbally or non-verbally) to guide the next steps. Staff then informs the researcher.
  - Depending on the situation, it may or may not be appropriate to ask the resident again later if they would like the opportunity to get involved., The caregiver will reapproach in 3-5 minutes, again check if the person is comfortable, and make any adjustments to improve comfort. Care staff will seek consent again. If consent is not given a second time, the DWS will be dropped and the usual ADL routine will begin.
- Assessments, tools  

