  - ADL checklist: toothbrushing, grooming, face wiping, taking medications
  - Was the activity completed?
- Subject's responses to the ADLs (multiple choice and text box)
  - Subject's autonomy to the activity (Likert scale of 1- 4)
  - Subject's attitude to the activity (Likert scale of 1- 4)
- At the end of the baseline studies, staff complete an ADCS-ADL score sheet for

each of their residents to provide longitudinal comparisons (31).

- Data collected during the Intervention phase

Reporting on The DevaWorld App's Feasibility (Aim 1)

- The DW app captures screen interactions, durations, end-of-session emoticons for self-assessment and end-of-session comments (choice of spoken or text input).
- The tablet's built-in camera records the dyad's expressions and exchanges during the session. These videos support analysis of engagement and reaction, and create a unique data set for developing speech emotion recognition system for future product upgrades.
- Occasionally research staff may also capture video and audio using an iPhone during DWS for capturing other nuances of the dyad engagement.
- In addition, at end of shift, staff complete a web-based questionnaire that
  - measures tolerance and acceptance of DevaWorld
  - records observations of resident's post and pre-post disposition
- Questions are a mix of multiple choice, 5-point Likert scales and free text
- Computers are located at the nurse station.

Reporting on Usual ADLs, following Intervention (Aim 2)

- Staff's usual reporting at the end of each shift.
- Additional: the survey website.
  - Subject name
  - Which ADLs were done (checklist)?
  - Time taken to start and finish
- Subject's responses to the ADLs (multiple choice and text box)
  - Autonomy to the activity (Likert scale of 1- 4)
  - Attitude to the activity (Likert scale of 1- 4)
- End of study
  - Residents will repeat Quality of Life and Response Behavior outcome measures (same ones as used in Baseline).
  - Participating staff will complete an ADCS-ADL scores sheet for each of their residents to provide longitudinal comparisons
  - Participating staff will undertake a 5 min exit interview at the conclusion of the trial. The interview will supplement and facilitate the interpretation of quantitative data gathered during including any post and pre-post concerns over the course of the study, which may provide further insights (32).

*iii. Explain training of individuals performing procedures*

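### The acceptability ratio in section IX names neither its score nor its denominator; on the natural reading, refused sessions drop out and the ratio is biased upward

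*Combined protocol and SAP*

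**What the plan says.** Section IX (Analysis Plan) gives the acceptability measure in one sentence: "The ratio of positively graded scores per dyad will be calculated to obtain the level of satisfaction of dyads and indicate the acceptability of DWS". It adds no score, cut-off, denominator or rule for sessions that did not take place.

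Three sources in section VI.c.ii could supply a grade:

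- **The resident's own rating.** The app captures "end-of-session emoticons for self-assessment and end-of-session comments". The timing is stated: "Upon completion of a session, the care staff assists the resident, if needed, to select an emoticon on the end screen before ending the DWS".
- **The staff end-of-shift questionnaire.** It "measures tolerance and acceptance of DevaWorld" and includes 5-point Likert items. The protocol does not say whether it is filled in for a refused session.
- **The daily report.** "Staff will record the resident's attitude to the DWS in their daily report". The text then describes how refusal may be expressed. Nothing links this report to the ratio.

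On refusal, section VI.c.ii (Consent/No consent) says: "If consent is not given a second time, the DWS will be dropped and the usual ADL routine will begin". Under process consent, staff also stop a session when the resident withdraws during it.

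Two other Aim 1 measures bear on this. Section V.d sets a DWS-participation rate above 55% as a primary outcome. Section IX puts a completion rate above 55% in its place and defines completion as the dyad remaining for all eight weeks.

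**The concern.** Aim 1 is to demonstrate tolerability and acceptability within the dyad. The most direct signs of non-acceptance that the protocol lists are refusals: pushing the tablet away, turning away, showing no interest. If the ratio is taken over grades given and the grade is the emoticon, those events contribute nothing to numerator or denominator. The ratio then describes satisfaction on the days when the resident was willing, and it flatters most the residents who were willing least often.

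Leaving the score and denominator open adds a second problem. The choice could be made after the data are seen, and the candidate definitions can give very different answers from the same sessions.

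**Working it through.** The plan gives no target, expected value or worked example for this ratio, so there is no stated figure to reproduce. The check compares the two candidate denominators.

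**Inputs from the protocol (section VI.c.ii)**

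- Two sessions per resident per week for six weeks: S = 2 x 6 = 12 scheduled sessions.
- The emoticon is selected only on completion of a session.
- A session declined twice is dropped, so it has no end screen.

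**Formulas**

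Let A be the sessions accepted and graded, P those graded positive, and S the scheduled sessions, all taken as offered.

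- Graded-only ratio: g = P/A.
- Offered-session ratio: P/S = (A/S) x (P/A) = a x g, where a = A/S is the share accepted.
- Overstatement by the graded-only ratio: g - a x g = g(1 - a). This is zero only if nothing is refused or nothing is graded positive.

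**One resident, every accepted session graded positive**

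| Accepted of 12 | Refused | Graded-only | Of scheduled |
|---|---|---|---|
| 1 | 11 | 1/1 = 100% | 1/12 = 8.3% |
| 2 | 10 | 2/2 = 100% | 2/12 = 16.7% |
| 5 | 7 | 5/5 = 100% | 5/12 = 41.7% |
| 7 | 5 | 7/7 = 100% | 7/12 = 58.3% |

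A resident who refuses all 12 has 0/0, so the graded-only ratio does not exist for that dyad.

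**Group level, assuming g = 0.90.** The documents give neither a nor g; the values are illustrative and show a range.

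| Share accepted, a | Graded-only | a x g | Overstatement, points |
|---|---|---|---|
| 0.25 | 90% | 22.5% | 67.5 |
| 0.55 | 90% | 49.5% | 40.5 |
| 0.80 | 90% | 72% | 18 |
| 0.90 | 90% | 81% | 9 |

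**Does another analysis in section IX catch refusals?** Completion is defined by staying eight weeks, not by sessions accepted. Withdrawal for refusal needs seven days of refusal in a row and is written for a resident who no longer wants to be in the study. A resident who declines sessions intermittently is not removed by that rule. Such a resident can therefore be a completer and also score 100% on the graded-only ratio. The participation rate in section V.d might reflect refusals, but its denominator is not defined and section IX does not carry it forward.

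**The case against.** The strongest objection is that section IX does not say the grade is the emoticon. It speaks of scores per dyad, and a dyad includes the staff member. The end-of-shift questionnaire is listed under Aim 1 and is not stated to depend on a completed session. Either that questionnaire or the daily attitude report could record a refusal as a negative grade. This stands: the upward bias is conditional on the reading. It does not remove the gap, because no text says that refusals enter the ratio from any source.

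Second, a reader might infer that the ratio cannot show poor acceptability at all. The documents do not support that. Even on the emoticon reading, a negative emoticon lowers the ratio; what is lost is poor acceptability expressed as refusal.

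Third, a reader might infer that the plan ignores refusal altogether. That also goes too far. The participation rate in section V.d may reflect it, and a resident who is withdrawn after sustained refusal counts against completion. Nor is the ratio itself one of the Aim 1 success criteria in V.d or IX. Intermittent refusal still escapes the analyses in IX.

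Fourth, uptake and satisfaction among users are different quantities, and a single composite hides which of them is low. This is fair, and it is a reason to report both components beside the composite.

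Finally, it would be wrong to count every session that the resident brings to an end as a failure. The protocol makes resident-led ending the normal close, followed by the emoticon. Only an ending by withdrawal of consent is evidence of non-acceptance.

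**Conclusion.** The point holds in conditional form. It is certain that section IX leaves the score, the positive cut-off and the denominator undefined and has no rule for refused sessions. If the ratio is positive emoticons over emoticons given, which is the natural reading, it overstates acceptability by g(1 - a). It can then reach 100% for a resident for whom only 2 of 12 scheduled sessions (17%) were accepted and positive.

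The 12-session arithmetic follows from the protocol's schedule and assumes that every scheduled session was offered. The group-level figures rest on assumed acceptance shares and an assumed 90% positive share; they show how the bias behaves and do not predict this trial's result. This should be corrected before analysis, since acceptability is one of the two components of feasibility in Aim 1.

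**What to change.** In section IX:

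1. Name the graded score and state which values count as positive.
2. Make the primary acceptability ratio, per resident, the positively graded sessions divided by all scheduled sessions that were offered. List separately the extra daily offers that the protocol provides for residents who wish to leave, so that they do not enlarge the denominator.
3. Count twice-refused sessions, and sessions ended by withdrawal of consent under process consent, as not positive. Sessions that close normally at the resident's pace keep their grade.
4. Leave sessions not offered for staffing or technical reasons out of the denominator, and list them with reasons.
5. Report the session participation rate and the graded-only ratio alongside as secondary measures, so that refusal and dislike can be told apart.
6. Reconcile the participation rate in section V.d with the completion rate in section IX, and give the denominator of each.

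The cost is small but not nil. Staff already record attitude daily, but the protocol does not require a session-level log. The existing report therefore needs an explicit field for offered, refused or withdrawn, with the reason when a session was not offered. The reported acceptability figure will be less favourable wherever sessions are refused.

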Training sessions will take place after baseline studies as knowledge transfer before or during baseline may introduce a bias. Staff will be shown the DevaWorld app and how to work optimally with it.

This will be a hands-on lesson with staff sharing one device between them alternating staff and resident roleplays. Mentia's instruction guide, 'How to get the most out of your DevaWorld Session' and training videos will be the basis of the training. Staff will also be guided on environmental aspects such as the best time and place, how to set up and introduce the DWS, and how to transition from the session to the ADL.

Each site will have a highly-trained internal champion, who will attend training and provide on-going support to staff throughout the study

Agenda for group training session.

- Introduction to the study aims and their critical role.
- Instruction on DevaWorld usage with a focus on the ADL content.
- A short review to identify any knowledge gaps.
- Follow-up sessions will be scheduled as needed.
- Break
- Study Protocol covering consent, scheduling, reporting, risks
- 5-minute pre-intervention interview so that we can learn about any potential barriers to participation in, or adherence to, clinical trial requirements.

iv. *Be clear about the difference between what is standard (if there were no evaluation study) and what is done specifically for the study.*

As a single arm study, the distinction we believe the distinction will be clear, i.e., care shift with usual care and the intervention, and care shift usual care and no intervention.

During the 6-week intervention part of study; on both intervention and no-intervention days, staff are encouraged to modify their practice according to any insights they derive from the study. They will be asked to note any modifications in their end-of-shift report.

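### Section IX makes a significant completer versus non-completer difference a condition of Aim 1 success; that describes who left, does not show tolerability, and is impossible to meet if every dyad completes

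*Combined protocol and SAP*

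**What the plan says.** Section IX sets the Aim 1 rule: "Successful primary outcomes are >55% completion rate and a statistically significant difference between assessments of completers and non-completers". It presents this as evidence of tolerability and acceptability. The same section defines completion: "Completion rates will be the percentage of all dyads who complete the entire eight weeks of study". Its list of statistical methods calls for a superiority test and says "P-values calculated by t-test, 1 sided". It does not say which assessments are compared between completers and non-completers, at what time, or which group should score better. It also does not say what happens if non-completers are few or absent.

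Section IX separately defines an acceptability measure: "The ratio of positively graded scores per dyad will be calculated to obtain the level of satisfaction of dyads".

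Section V.d states the Aim 1 rule in other terms. It asks for a participation rate above 55% and "a statistically significant difference between assessments of DWS-participation and non-participation, indicating tolerability and acceptability of routine DWS". The unit of non-participation (resident, session or day) is not given. Section VI.c.iv speaks of staff practice "on both intervention and no-intervention days", so a day-level reading of V.d is possible.

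Under VI.c.ii, the first two of the eight weeks are without the product: "In the first two weeks of the study to establish baseline, dyads will undertake usual ADL care, i.e., without the DevaWorld Session (DWS) intervention". The same section schedules the repeat quality-of-life and response-behavior measures at end of study only.

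**The concern.** Because there is one arm, completers and non-completers are defined by what happens after enrolment. If their baseline or common-time assessments differ, attrition was selective. If it is their session ratings that differ, those who left rated the sessions differently. Neither result shows that the residents as a group tolerated or accepted DWS.

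The grouping is also only loosely tied to the product. A dyad lost during the two baseline weeks counts as a non-completer without having had a DWS. Residents who leave may lack the end-of-study measures. Session, shift and biweekly data up to withdrawal may exist, but the plan does not say whether those are the assessments it means.

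The second condition works against the first. The better the retention, the smaller the non-completer group and the weaker the test, until with no non-completers there is no test at all. What is at stake is the primary conclusion: a product that residents tolerate well could be declared infeasible by the plan's own rule. The >55% criterion guards against the opposite error.

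**Working it through.** **Inputs from the documents.** Enrolment is 40, allowing for 20% dropout, with 32 evaluable (VI.a.i). This reproduces: 32 / (1 − 0.20) = 40. The plan's expected split is therefore 32 completers and 8 non-completers. The threshold is >55%; 0.55 × 40 = 22, so at least 23 of 40 must complete.

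**Assumptions, because the plan gives no alpha, effect size or unit for this test.** One independent value per resident, available for all 40; two-sample t-test; one-sided alpha 0.05; true differences of 0.5 and 0.8 SD as illustrations, held fixed across completion rates.

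**Step 1: power of the second condition.** With n1 completers and n2 = 40 − n1 non-completers, the test has 38 degrees of freedom and noncentrality d × √(n1·n2/40). At 32/8 the multiplier is √(32 × 8/40) = 2.53; at 38/2 it is √(38 × 2/40) = 1.38.

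| Completers / non-completers | Power, 0.5 SD | Power, 0.8 SD | Difference for 80% power, one-sided | Same, two-sided 0.05 |
|---|---|---|---|---|
| 23 / 17 (lowest passing split) | 0.46 | 0.79 | 0.81 SD | 0.92 SD |
| 32 / 8 (planned dropout) | 0.34 | 0.63 | 1.00 SD | 1.14 SD |
| 36 / 4 | 0.24 | 0.44 | 1.33 SD | about 1.5 SD |
| 38 / 2 | 0.17 | 0.29 | 1.84 SD | about 2.1 SD |
| 40 / 0 | no test | no test | none | none |

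**Step 2: chance of meeting both conditions.** For true completion rate p, sum over k = 23 to 39 the Binomial(40, p) probability of k completers times the power at k versus 40 − k. The outcome k = 40 counts as failure because no test exists.

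| True completion | >55% alone | Both, no difference | Both, 0.5 SD | Both, 0.8 SD |
|---|---|---|---|---|
| 55% | 0.44 | 0.02 | 0.19 | 0.34 |
| 70% | 0.97 | 0.05 | 0.39 | 0.70 |
| 80% | about 1 | 0.05 | 0.34 | 0.62 |
| 90% | about 1 | 0.05 | 0.23 | 0.42 |
| 95% | about 1 | 0.04 | 0.15 | 0.26 |
| 100% | 1 | 0 | 0 | 0 |

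The joint chance is not monotone. It rises to a maximum near 70% true completion and then falls as retention improves.

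**Step 3: V.d beside IX.** If non-participation in V.d means sessions or days without DWS, the comparison could be made within residents. Non-participation would then exist even with full retention, and neither the impossibility nor the tables above would apply to that version. They apply to section IX as written.

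**The case against.** The strongest reply is that 40/40 is nearly hypothetical. The chance of it is 0.80^40 = 0.0001 at the plan's expected completion, 0.90^40 = 0.015 at 90% and 0.95^40 = 0.13 at 95%. Dyads can also be lost for reasons unrelated to DWS, including staff absence, so some non-completers could exist even if every resident tolerated it. This is fair as to 40/40, but it does not rescue the rule. If losses are unrelated to DWS, the two groups should not differ, and the rule then passes at most about 5% of the time.

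Second, selective attrition is the exact label only for baseline or common-time measures; for session ratings the difference means that leavers rated DWS differently. That nuance stands, but it is still not evidence of tolerability in the group.

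Third, the superiority test listed in section IX may imply a direction. It does not name the group expected to be better, and it is unclear whether that list covers Aim 1 at all.

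Fourth, V.d may be the intended rule. That is possible, but it does not repair section IX, and its own unit is undefined.

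Fifth, the figures are conditional. They ignore missing assessments and the sharing of one staff member among several residents, and the effect sizes have no source in the documents. The tables are therefore illustrative. The impossibility at 40/40, and the ceiling at about alpha when the groups do not differ, do not depend on the assumed effect size.

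**Conclusion.** The concern holds for section IX. The second condition does not measure what the plan says it indicates, and it can turn a good feasibility result into a failure. At the plan's own 20% dropout, the chance of declaring Aim 1 successful is 0.34 (0.5 SD) or 0.62 (0.8 SD), against about 1 for the completion criterion alone. With no true difference it is at most 0.05 at every completion rate, and with full completion it is 0. These figures rest on 40 independent residents each with one usable value, a one-sided alpha of 0.05 and the assumed differences. This must be fixed before data are seen, because it sits in the primary success rule.

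**What to change.** In section IX, remove the completer versus non-completer significance test from the Aim 1 success rule and keep the >55% criterion. Judge acceptability on the ratio of positively graded scores per dyad, reported with a 95% confidence interval in all residents offered a DWS. If the sponsor wants a pass mark for that ratio, set it before data are seen. Compare completers with non-completers only descriptively, on baseline variables.

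Reconcile V.d with IX so that there is one primary rule. If a participation versus non-participation contrast is kept, define its unit and direction, and do not present it as evidence of tolerability.

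The cost is a change of wording in the protocol and analysis plan; no new data are needed.
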